#### 6.10.1.3. Unexpected Adverse Event

An unexpected AE is any AE that is not identified in nature, severity, or frequency in the current **IB** or product information.

#### 6.10.1.4. Unexpected Adverse Drug Reaction

An adverse drug reaction (ADR) is an adverse reaction, the severity of which is not consistent with the applicable product information or **IB**. All noxious and unintended responses to a medical product related to any dose should be considered an ADR.

- The phrase “responses to a medicinal product” means that a causal relationship between a medicinal product and an AE is at least a reasonable possibility (meaning the relationship cannot be ruled out).
- The expression “causal relationship” is meant to convey that, in general, there are facts, evidence, or arguments to suggest a reasonable causal relationship. All serious and unexpected ADRs will have expedited reporting to regulatory agencies following ICH requirements.

#### 6.10.2. Adverse Event Reporting Period

The AE reporting period for this study begins upon receiving the first dose of study treatment during the Imaging Period and ends during the Imaging Follow-up Period. If a subject experiences an AE after signing the informed consent, but prior to receiving study drug, the event will NOT be collected unless the investigator feels the event may have been caused by a protocol procedure. Likewise, if a subject experiences an AE during the Post-Op Follow-up Period, the event will NOT be collected unless the investigator feels the event may have been caused by a protocol procedure.

All AEs (both serious and non-serious) must be assessed through the Imaging Follow-up Period. All measures required for AE management and the ultimate outcome of the AE must be recorded in the eCRF and reported to the Sponsor. All study-drug related AEs must be followed until resolution, the return to baseline, or until the event is deemed stable or irreversible.

In addition, any known untoward event that occurs subsequent to the AE-reporting period that the investigator assesses as related to the study drug should also be reported as an AE and must be recorded in the eCRF.

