#### 5.1.2. Active Comparator

The active comparator (reference standard) is  $^{133}\text{Xe}$  gas.

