#### 6.10.3. Recording Adverse Events

When an AE/SAE occurs, it is the responsibility of the Investigator to review all documentation (e.g. hospital progress notes, laboratory, and diagnostic reports) relative to the event. The Investigator will then record all relevant information regarding an AE/SAE in the eCRF. All details of any treatments initiated due to the AE should also be recorded in the subjects' notes and the eCRF.

All AEs will be documented in the appropriate section of the eCRF. Among these AEs, all SAEs (refer to [Section 6.10.1.2](#)) will be additionally documented in an SAE Report. The following will be recorded for each event on the eCRF:

- A description of the AE in medical terms, not as reported by the subject. Whenever possible, a diagnosis should be given when signs and symptoms are due to common etiology (e.g., cough, runny nose, sneezing, sore throat, and head congestion should be reported as “upper respiratory infection”).
- The date of onset (start date).
- The date of resolution (stop date).
- The severity as assessed by the investigator according to the definitions in [Section 6.10.4](#).
- The causal relationship to study drug as assessed by the investigator; the decisive factor in the documentation is the temporal relation between the AE and the study drug (refer to [Section 6.10.5](#)).

- Action taken for study drug (none, study drug discontinued, study drug dose reduction, study drug delayed).
- Other action(s) taken (none, concomitant medication given, new or prolonged hospitalization, procedural surgery).
- The outcome according to the following definitions:
  - Recovered with sequelae;
  - Recovered without sequelae;
  - Ongoing, no therapy;
  - Ongoing, therapy;
  - Died, or
  - Change in toxicity grade/severity.
- Serious Adverse Event (as defined in [Section 6.10.1.2](#)): yes or no.

If, in any subject, the same AE occurs on several occasions (unless the AE is continuous and of stable grade), then the AE in question will be documented and assessed each time. For an SAE, the information listed above to be recorded in the eCRF will also be recorded in the SAE Report. Only AEs that fulfill the criteria for SAEs (refer to [Section 6.10.1.2](#)) should be recorded in the SAE Report.

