### 8.8. Safety Analysis

All safety analyses will be performed on the Safety population, unless otherwise stated.

AEs will be coded using MedDRA terminology. Events are defined as AEs if they start or worsen after a subject's administration of study drug. All AEs will be summarized by SOC, preferred term, severity and relationship to study drug. AEs leading to death or to discontinuation from study drug and SAEs will also be tabulated. In the by-subject summary, a subject having the same event more than once will be counted only once and by greatest severity.

Vital signs, including change from baseline, will be summarized.

Prior and concomitant medications will be coded using the World Health Organization (WHO) Drug dictionary. Concomitant medications will be summarized descriptively. The summary tables will show the number and percentage of subjects by preferred term. Subjects who take the same medication (in terms of the preferred term) more than once will only be counted once for that medication. Prior and concomitant medications will be listed separately.

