| Adverse Events (AE)                   |                        | X                    | X                              |                    |
| Local Laboratory Tests                            |                        |                      |                                |                    |
| Serum Pregnancy Test                  | X                      |                      |                                |                    |

Abbreviations: AE = adverse event; eCRF = electronic case report form; FEV1 = forced expiratory volume; MRI = magnetic resonance imaging; SpO2 = arterial oxygen saturation.

 Screening and Imaging study periods can occur on the same day or on different days, however there should be ≤48 hours between administration of the study drug and reference standard scans.

 The Follow-Up period will occur on the day after (+3 days) the completion of all imaging and prior to resection surgery.

 Medical history will include any pulmonary function values (i.e. FEV1) from the subject files as well as smoking history.

 FEV1 measurement should occur prior to administration of the study drug and reference standard scans.

 Vital Signs (including heart rate, respiration rate, temperature, and blood pressure) will be assessed before and after each scanning session (both Xe and Xe). Subjects will have a 5-minute rest in a supine position before vital signs are assessed.

 Changes in heart rate of greater than ±20% are considered significant. If the subject is to receive another dose, the next dose will not be administered until the heart rate is within 20% of its baseline value. If the subject has received their last dose, they will be observed until their heart rate is within 20% of its baseline value. The subject will be monitored for the duration of the MRI exam by a qualified medical professional.

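### Protocol Section 6.10.2 gives two different start points for adverse-event collection, and they disagree for subjects who receive 133Xe first

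*Protocol*

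**What the plan says.** Protocol Section 6.10.2 opens with: "The AE reporting period for this study begins upon receiving the first dose of study treatment during the Imaging Period". Section 5, headed Study Treatments, covers both gases, so a dose of either one opens the period.

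The next sentence of 6.10.2 turns to AEs that occur after consent: "but prior to receiving study drug, the event will NOT be collected". The one exception is for events that, in the investigator's view, a protocol procedure may have caused.

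The two terms are not interchangeable in the protocol. Section 5.1.1 says that the study drug is hyperpolarized 129Xe. Section 5.1.2 names 133Xe separately: "The active comparator (reference standard) is" 133Xe gas. Footnote 1 of Appendix 1 keeps them apart when it limits the time "between administration of the study drug and reference standard scans" to 48 hours.

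Section 8.8 repeats the narrower term for the analysis: "Events are defined as AEs if they start or worsen after a subject's administration of study drug".

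Section 5.4 randomizes subjects 1:1 to the two orders, so about half receive 133Xe before any study drug in the sense of Section 5.1.1.

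**The concern.** In a 133Xe-first subject, take an event that starts after 133Xe and before 129Xe. The first sentence of 6.10.2 puts it inside the reporting period. The second sentence puts it outside unless it is attributed to a procedure. Section 8.8 also puts it outside unless it worsens later, and has no procedure exception. In a 129Xe-first subject, an event in the same interval is inside under every one of these rules.

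The SAP (Section 4.6.1) lays out its treatment-emergent AE tables by sequence and overall. If the narrower wording were applied, one sequence column would hold all-cause events from the first gas onward. The other would hold all-cause events only from the second gas, plus procedure-attributed events before it. Part of any difference between the columns could then come from the collection rule. The analysis cannot repair this, because an event that was never collected cannot be tabulated.

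The narrower wording also collides with serious-event reporting. The second sentence of 6.10.2 makes no exception for serious events, while 6.10.7 requires a serious event in this same interval to be reported within 24 hours, whatever its relationship to the drug.

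**Working it through.** The plan states no figure on this point, so the check sets the texts side by side and then works out the length of the interval at issue.

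**Step 1. Which events between the two gases count?**

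| Rule | 129Xe first | 133Xe first |
|---|---|---|
| 6.10.2, first sentence (*study treatment*) | collected | collected |
| 6.10.2, second sentence (*study drug* = 129Xe) | collected | not collected, unless attributed to a protocol procedure |
| 8.8 (*study drug* = 129Xe) | an AE | not an AE, unless it worsens after 129Xe |
| 6.10.7 (serious events, *study treatment*) | reported | reported |
| 8.2 Safety set (a dose of either gas) | subject included | subject included |

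Only the second and third rows treat the two orders differently.

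**Step 2. How many subjects?** 32 completers (Protocol 3.1) at 1:1 (5.4): 32 × 1/2 = 16 in the 133Xe-first order.

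**Step 3. How long is the interval?** Let *g* be the gap between the gases and *f* the time from the last scan to the follow-up call.

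- *g* is at most 48 hours (Appendix 1, footnote 1). The schedule puts both gases on Day 1, so shorter gaps are likely. A same-day gap of 1 to 4 hours is used below as an assumption.
- *f* is the day after imaging, plus up to 3 days (Appendix 1, footnote 2), or about 24 to 96 hours.

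With a start at the first gas, both orders have all-cause observation of *g* + *f*. With a literal start at 129Xe, the 129Xe-first order still has *g* + *f*, but the 133Xe-first order has *f* only. The share of all-cause observation lost in that order is *g* / (*g* + *f*):

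| *g* | *f* = 24 h | *f* = 96 h |
|---|---|---|
| 1 h (assumed) | 1/25 = 4% | 1/97 = 1% |
| 4 h (assumed) | 4/28 = 14% | 4/100 = 4% |
| 48 h (maximum) | 48/72 = 67% | 48/144 = 33% |

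These are shares of time, not of events. Under 6.10.2, events attributed to a procedure are kept even on the literal reading.

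**Step 4. After the fix.** With the start at the first dose of either gas, both orders have *g* + *f*, for example 48 + 24 = 72 hours each. The difference is 0.

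**The case against.** The strongest reply is that the first sentence of 6.10.2 is the one that sets the period, and that the second was meant only for the time between consent and first dosing. Much of the text supports this. Section 3.1 has AE information collected throughout the Imaging period and safety monitored after both gases. Section 6.10.7 starts serious-event reporting at the first study treatment. The Safety set takes a dose of either gas. The AE row in Appendix 1 does not separate the gases. SAP 4.6.2 uses *study drug scan* for both, which suggests that the sponsor uses the term loosely. All of this stands. It shows what was probably intended, but it does not change an explicit instruction not to collect, written with a term that the protocol defines otherwise.

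The reply also limits the consequences. Four stronger readings are tempting, and the documents do not support them:

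- *That the window is in fact cut off at 129Xe and the sequences are observed unequally.* This follows only if someone applies the narrower sentence against the provisions above.
- *That a subject who withdraws after 133Xe alone can have no AE in the tables.* Section 8.8 alone would imply this, but SAP 4.6.1 tabulates every reported AE as treatment-emergent, with no filter on onset after 129Xe.
- *That the records could not place an event relative to each gas.* Section 6.10.3 lists an onset date and no clock time. The eCRF itself is not among the documents, however, and SAP 4.6.1 shows that relationship to each scan procedure is judged, an item that 6.10.3 does not list.
- *That a number of missed subjects can be given.* The documents contain no event rate for the interval. The only figure is that no treatment-emergent AEs were reported in 103 people given 129Xe (Protocol 1.5). There is none for 133Xe.

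Finally, the safety objective concerns 129Xe, and events that start or worsen after 129Xe are collected in both orders on any reading. No between-sequence test of AEs is planned.

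**Conclusion.** The contradiction is real. Section 6.10.2 gives two start points, 8.8 repeats the narrower one, and 6.10.7, 3.1 and the Safety set follow the broader one. The rules disagree only for the interval between the gases in the 133Xe-first order.

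The exposure is about 16 of 32 subjects, assuming exact 1:1 allocation among completers. The interval is at most 48 hours. On the literal reading, the loss of all-cause observation time in that order is 33% to 67% at the maximum gap and 1% to 14% at assumed gaps of 1 to 4 hours. On the *study treatment* reading it is 0. What is at risk is events not attributed to a procedure, and only where the narrower wording is actually applied. The documents do not show that it was. The effect on conclusions about 129Xe safety is likely to be small. The point deserves correction because the loss would fall on one sequence only and could not be recovered in the analysis.

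**What to change.** In Protocol 6.10.2, change the cut-off in the second sentence from receipt of study drug to *receipt of the first dose of either 129Xe or 133Xe*. In 8.8, define AEs as those that start or worsen after the *first dose of either gas*. Both sections then agree with 6.10.7 and the Safety set, and the two sequences share one start point. The SAP tables need no change.

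The cost is two reworded sentences and a few more AE entries in 133Xe-first subjects. If subjects have already been imaged under the present wording, the change cannot recover uncollected events, and the sponsor should document which start point the sites used.

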#### 6.10.3. Recording Adverse Events

When an AE/SAE occurs, it is the responsibility of the Investigator to review all documentation (e.g. hospital progress notes, laboratory, and diagnostic reports) relative to the event. The Investigator will then record all relevant information regarding an AE/SAE in the eCRF. All details of any treatments initiated due to the AE should also be recorded in the subjects' notes and the eCRF.

All AEs will be documented in the appropriate section of the eCRF. Among these AEs, all SAEs (refer to [Section 6.10.1.2](#)) will be additionally documented in an SAE Report. The following will be recorded for each event on the eCRF:

- A description of the AE in medical terms, not as reported by the subject. Whenever possible, a diagnosis should be given when signs and symptoms are due to common etiology (e.g., cough, runny nose, sneezing, sore throat, and head congestion should be reported as “upper respiratory infection”).
- The date of onset (start date).
- The date of resolution (stop date).
- The severity as assessed by the investigator according to the definitions in [Section 6.10.4](#).
- The causal relationship to study drug as assessed by the investigator; the decisive factor in the documentation is the temporal relation between the AE and the study drug (refer to [Section 6.10.5](#)).

- Action taken for study drug (none, study drug discontinued, study drug dose reduction, study drug delayed).
- Other action(s) taken (none, concomitant medication given, new or prolonged hospitalization, procedural surgery).
- The outcome according to the following definitions:
  - Recovered with sequelae;
  - Recovered without sequelae;
  - Ongoing, no therapy;
  - Ongoing, therapy;
  - Died, or
  - Change in toxicity grade/severity.
- Serious Adverse Event (as defined in [Section 6.10.1.2](#)): yes or no.

If, in any subject, the same AE occurs on several occasions (unless the AE is continuous and of stable grade), then the AE in question will be documented and assessed each time. For an SAE, the information listed above to be recorded in the eCRF will also be recorded in the SAE Report. Only AEs that fulfill the criteria for SAEs (refer to [Section 6.10.1.2](#)) should be recorded in the SAE Report.

#### 6.10.4. Assessing Adverse Event Severity

To ensure there is no confusion or misunderstanding of the difference between the terms “serious” and “severe”, which are not synonymous, the following note of clarification is provided:

The term “severe” is often used to describe the intensity (severity) of a specific event (as in mild, moderate, or severe myocardial infarction); the event itself, however, may be of relatively minor medical significance (such as severe headache).

This is not the same as “serious”, which is based on subject/event outcome or action criteria usually associated with events that pose a threat to a subject’s life or functioning. Seriousness (not severity) serves as a guide for defining regulatory reporting obligations.

All AEs are to be evaluated with respect to severity using:

- Mild;
- Moderate, or
- Severe.

#### 6.10.5. Assessing Adverse Event Relationship to Study Drug

The investigator (or sub-investigator) must record his/her opinion concerning the relationship of the AE to study treatment on the eCRF. Investigators will determine relatedness of an event to

study drug based on a temporal relationship as well as if the event is unanticipated or unexplained given the subject's clinical course, previous medical conditions, and concomitant medications. An event should be recorded as "drug related" if the investigator believes it to be reasonably related to study drug.

#### 6.10.6. Reporting Adverse Events

Each AE is to be classified by the investigator as serious or non-serious. This classification determines the reporting procedures to be followed ([Table 1](#)).

**Table 1 Reporting Requirements for Adverse Events**

| Gravity | Reporting Time         | Type of Report |
|----------------|-------------------------------|-----------------------|
| Serious        | Within 24 hours               | Complete AE eCRF      |
| Non-serious    | Per eCRF submission procedure | Appropriate AE eCRF   |

#### 6.10.7. Reporting Serious or Unexpected Adverse Events

Any SAE, irrespective of the relationship to Study Drug, that occurs during the course of the study (from the first dose of study treatment during the Imaging Period up to and including the Imaging Follow-up Period) will be reported on the eCRF as soon as possible (within 24 hours after the site becomes aware of the event).

The investigator is encouraged to discuss with the Pharmacovigilance group any AE for which the issue of reportability is unclear or questioned.

An SAE Report should be prepared, containing as much available information concerning the event as possible, so that a written report can be filed with the appropriate regulatory authorities. If causality cannot be definitively assessed at the time of the SAE, it is important to notify the Sponsor, or its designee, within the timelines stated in [Table 1](#). When new significant information is obtained, and the outcome and attribution of the event is known, the investigator will communicate this on the eCRF. The relevant information will be provided in a timely manner to allow reporting to regulatory authorities within the required reporting period.

For a follow-up report to the regulatory authorities, the Sponsor may be required to collect further information for a detailed description and a final evaluation of the case, including copies of hospital reports, autopsy reports, or other relevant documents. Any SAE follow-up information requested by the Sponsor (or its designee) should be provided in a timely manner to ensure that the SAE report is made to regulatory authorities within the requested timeframe.

The Investigator, or Sponsor where applicable, will notify the relevant Institutional Review Board (IRB) of any SAEs and safety reports according to local regulation requirements.

#### 6.10.8. Follow-Up of Adverse Events

All AEs (both serious and non-serious) should be followed through the end of the observation period or until resolution, whichever is longer. All measures required for AE management, as well as the ultimate outcome of the AE, must be recorded in the source document and reported to the Sponsor.

#### 6.11. Removal of Subjects from the Study or Study Drug

The investigator may withdraw a subject from study participation for any of the following reasons:

- A significant protocol violation occurs;
- A serious or intolerable AE occurs;
- The sponsor or investigator terminates the study, or
- The subject requests to be discontinued from the study.

#### 6.12. Discontinuation of Study Sites

Study site participation may be discontinued if the Sponsor, investigator, or the IRB of the study site judges it necessary for any reason.

#### 6.13. Discontinuation of the Study

The study will be discontinued if the Sponsor judges it necessary for any reason.

#### 6.14. Appropriateness of Measurements

All procedures and assessments used to evaluate the safety and efficacy of hyperpolarized  $^{129}\text{Xe}$  are widely used and generally regarded as reliable, accurate, and relevant. Pulmonary function tests are used to evaluate potential post-operative risks and complications in patients considering lung surgery (Wang, 2004). The specific tests used in this protocol to assess pulmonary function, FEV1, and ventilation assessments, are both commonly used assessments in this patient population.

### 7. QUALITY CONTROL AND ASSURANCE

A study start-up/investigator training will be held for all sites prior to first subject enrollment. To ensure accurate, complete, and reliable data, the Sponsor or its representatives will:

- Provide instructional material to the study sites, as appropriate.

- Conduct a start-up training session to instruct the investigators and study coordinators. This session will give instruction on the protocol, the completion of the eCRF, and study procedures.
- Make periodic visits to the study site.
- Be available for consultation and stay in contact with the study site personnel by mail, telephone, and/or fax.
- Review and evaluate eCRF data and use standard computer edits to detect errors in data collection.
- Conduct a quality review of the database.

In addition, the Sponsor or its representatives may periodically check a sample of subject data recorded against source documents at the study site. The study may be audited by the Sponsor or its representatives, and/or regulatory agencies at any time. Investigators will be given notice before an audit occurs.

To ensure the safety of participants in the study, and to ensure accurate, complete, and reliable data, the investigator will keep records of laboratory tests, clinical notes, and medical records in the subject's files as original source documents for the study. If requested, the Investigator will provide the sponsor, applicable regulatory agencies, and applicable ethical review boards with direct access to original source documents.

